7.4.4 Definition of variables, methods and scales to be used for the measurement

Variable	Conceptual Definition	Operational Definition	Measurement Type	Normal value	Statistical test
OSDI Score	OSDI is a questionnaire designed to establish a severity and Classification of dry eye according to its symptoms.	The evaluator will apply the questionnaire to the subject and allow the subject to answer it calmly without any pressure and/or coercion. See annex 16.1 OSDI .	Continuous quantitative	Score: OSDI= $\frac{\sum \text{score}}{25}$ n answers answered	
 • ANOVA of repeated measures. • One-way ANOVA*
TRLNI	Measurement of tear rupture time using non-invasive methods based on the observation of the film's mirror reflection in a grating design or in the placid discs of the corneal topographers and their analysis using specialized software.	The TRLNI will be measured by means of the Oculus Keratograph 5M.	Discrete quantitative	>10s	
 • ANOVA of repeated measures. • One-way ANOVA*
Corneal and conjunctival staining with lysmine green	Detection of epithelial defects in the conjunctiva and cornea.	Direct observation with slit lamp, graduation on Oxford scale. See annex 16.2 Oxford scale .	Ordinal Qualitative	Degrees: The stain is presented in a series of panels (A-E). The points Stains range from 0-5 for each panel and from 0-15 for the exposed toral area of the conjunctiva and cornea.	
 • χ^2 (Chi-square) of Pearson or Fisher's Exacta • McNemar Test*

Corneal and conjunctival staining with fluorescein	
Detection of epithelial defects in the conjunctiva and cornea.
	
Direct observation with slit lamp, graduation on Oxford scale. See annex 16.2 Scale of Oxford.
	
Ordinal Qualitative
	
Degrees: The stain is presented in a series of panels (A-E). The points Stains range from 0-5 for each panel and from 0-15 for the exposed toral area of the conjunctiva and cornea.
	
 • χ^2 (Chi-square) of Pearson or Fisher's Exacta • McNemar Test*
Conjunctival Hyperemia Changes	
It is defined as the simplest reaction of the conjunctiva to a stimulus, a red appearance is seen secondary to vasodilation of the conjunctival vessels of variable intensity.
	
Direct observation. Classification by Efron scale. See annex 16.3 Efron's scale.
	
Ordinal qualitative
	
Degrees: 0= Normal, 1= Very mild, 2= mild, 3= Moderate and 4= Severe
	
 • χ^2 (Chi-square) of Pearson or Fisher's Exacta • McNemar Test*
Incidence of chemosis	
It is defined as conjunctival edema resulting from an inflammatory reaction. It is classified as present or absent.
	
The evaluator will use a narrow beam of light at 60° and measure whether the conjunctiva separates by $\geq 1/3$ of the total palpebral aperture or whether it exceeds the gray line
	
Ordinal qualitative
	
Present/absent
	
 • One-way ANOVA • Pearson's χ^2 (Chi-square) or Fisher's Exact test
Incidence of AEs	
Any adverse medical event that occurs in a patient or clinical research subject who has been administered a pharmaceutical product and that does not
	
The AEs manifested during the conduct of the study will be collected using the FRCE.
	
Continuous quantitative Categorical qualitative
	
Frequency Subjects presenting EA/total number of subjects exposed. Intensity
 • Mild • Moderate • Severe Causality
	
One-way ANOVA Pearson's χ^2 (Chi-square) or Fisher's Exact test

- Probable
- Possible
- Unlikely

Changes BCVA	Spatial VA is the ability to distinguish separate elements of an object and identify them. It is quantified as the minimum angle of separation (located at the nodal point of the eye) between two objects that allows them to be perceived as separate objects	Snellen chart	Discrete quantitative	Fraction 0.6 to 2.0	ANOVA for repeated measures. • One-way ANOVA*
--------------	-----------------------------------------------------------------------------------------------------------------------------------------------------------------------------------------------------------------------------------------------------------------	---------------	-----------------------	-------------------------------	----------------------------------------------------------------

7.4.4.1 Adverse events

An AE is any unfavorable medical appearance in a patient who is administered a PI, regardless of causal attribution.

Management of AEs will be performed as described in the Adverse Events section. See point 8 Evaluation and management of adverse events.

The PI will record in the corresponding section of the electronic case report form (FRCE) the AEs that the patients in the study may present, in addition to referring them in the clinical file.

For an adequate evaluation of AEs, in addition to directed questioning, it is necessary to perform the Comprehensive Ophthalmological Evaluation at each visit, which consists of: the ophthalmological examination of the eyelids and adnexa; anterior and posterior segment that is performed in a routine ophthalmological examination, whose procedures are not specifically included in the study variables. Posterior pole evaluation can be with direct or indirect ophthalmoscopy, with or without pharmacological mydriasis, at the discretion of the PI. An assessment of the fundus will be carried out in search of abnormalities that alter the result of the study. IOP will be measured in this evaluation, with the PI choice instrument, it should be measured after the evaluation of stains. The result of the assessment will be recorded in the clinical file. In the electronic case report form (FRCE), only the findings that are considered so by the PI will be reported as AEs.

7.4.4.2 OSDI Score

OSDI is the most widely used symptomatic assessment tool in SOS clinical studies. It is referred to in the TFOS DEWS II as it is a diagnostic means already established among ophthalmologists.

It is a self-administering questionnaire of 12 questions, which is divided into three sections: frequency of symptoms, alteration of activities of daily living, worsening due to environmental factors in the last week. Each answer is assigned a numerical value which is then multiplied by 25 and then divided by the number of questions answered. The result can range from 0 to 100, classifying the severity of symptoms as specified below:

- < 12 = normal
- 13 – 22 = mild
- 23 – 32 = moderate
- ≥ 33 = severe

The OSDI score will be recorded in the FRCE.

Management as AE: A $\geq 40\%$ increase in the baseline OSDI score value should be reported and managed as an AE due to lack of efficacy.

7.4.4.3 Better Corrected Visual Acuity

Visual acuity (VA) is a test of visual function. Spatial VA is the ability to distinguish separate elements of an object and identify them. It is quantified as the minimum angle of separation (located at the nodal point of the eye) between two objects that allows them to be perceived as separate objects.

Snellen's notation is described as the distance at which the test is performed, divided by the distance at which the letter is vertically equivalent to 5 arc minutes. Thus, at 6 meters a letter 6/6 (20/20) is equivalent to 5 minutes of arc, a letter 6/12 (20/40) is equivalent to 10 minutes, and a letter 6/60

(20/200) equals 50 minutes. The Snellen fraction can also be expressed as a decimal (i.e., 20/20 = 1 and 20/40 = 0.5). [47]

VA will be evaluated at baseline, without refractive correction with the Snellen chart. It will be in a place with adequate lighting, natural or artificial, and at 3m from the patient to be evaluated. The visual acuity of each eye will be taken, starting with the right eye (OD) asking the patient to keep both eyes open and using an occlude to cover the left eye (OS); the patient will read aloud the lines that the evaluator points out, the line of smaller letters that he can see will be noted by the evaluator in fraction as the VA of OD in the clinical record. The OS is proceeded with the same method.

Subsequently, the patient's objective and subjective refractive correction will be performed. The result of the subjective refraction will be reported as CVMA, it will be noted in fraction in the clinical record and in the FRCE, in addition to the FRCE it will be noted in decimal. CVAM cannot be inferior to VA.

Management as EA: A decrease of more than 2 lines on the Snellen card must be reported and handled as EA.

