3.2 Secondary objectives

- To demonstrate the non-inferiority of Humylub Ofteno® PF compared to Hyabak® and Lagricel Ofteno® PF in the efficacy of the treatment of patients with dry eye, by means of the measurement of the LRLR.
- To demonstrate the non-inferiority of Humylub Ofteno® PF compared to Hyabak® and Lagricel Ofteno® PF in the efficacy of the treatment of patients with dry eye, by means of changes in corneal and conjunctival stains with fluorescein.
- To demonstrate the non-inferiority of Humylub Ofteno® PF compared to Hyabak® and Lagricel Ofteno® PF in the efficacy of the treatment of patients with dry eye, by changing corneal and conjunctival stains with lysmine green.
- To demonstrate the non-inferiority of Humylub Ofteno® PF compared to Hyabak® and Lagricel Ofteno® PF in the efficacy of the treatment of patients with dry eye, through changes in conjunctival hyperemia.
- To demonstrate the non-inferiority of Humylub Ofteno® PF compared to Hyabak® and Lagricel Ofteno® PF in the safety of the treatment of patients with dry eye, through the incidence of chemosis.
- To demonstrate the non-inferiority of Humylub Ofteno® PF compared to Hyabak® and Lagricel Ofteno® PF in the safety of the treatment of patients with dry eye, through the incidence of AEs.
- To demonstrate the non-inferiority of Humylub Ofteno® PF compared to Hyabak® and Lagricel Ofteno® PF in the safety of the treatment of patients with dry eye, by means of changes in CVAM.

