5.1.2 Exclusion Criteria

- Women who are pregnant, breastfeeding, or planning to become pregnant within the study period.
- Have participated in another clinical research study \leq 30 days prior to the screening visit.
- Have previously participated in this study.
- Have a CVAM of 20/200 or worse in one of the eyes.
- Present an ophthalmological diagnosis of:
 - o Allergic, viral, or bacterial conjunctivitis.
 - o Anterior blepharitis.
 - o Parasitic infestations in any ocular structure or its appendages.
 - o Unresolved eye trauma.
 - o Healing diseases of the ocular surface.
 - o Corneal or conjunctival ulcers.
 - o Filamentous keratitis.
 - o Neurotrophic keratitis.
 - o Bullous keratopathy.
 - o Neoplastic diseases on the ocular surface or adnexa.
 - o Diseases with fibrovascular proliferations on the conjunctival and/or corneal surface.

- Retinal and/or posterior segment diseases that require treatment or threaten visual prognosis.
- Glaucoma.
- Disorders of the eyelids that cause palpebral malpositions, limit the proper closing or opening of the eyelids, or are the cause of epiphora.
- Have a management of your dry eye that requires the implementation of all stage 2 treatments of the TFO DEWS II treatment and stage management recommendations for dry eye disease.
- Have a history of drug addiction or drug dependence current or within the last two years prior to signing the FCI.
- Have a history of eye surgical procedure within the last 3 months prior to signing the FCI.
- Be a soft or hard contact lens wearer. You will be able to enter in case of suspending its use during the study, you must comply with 15 days without using the contact lens prior to your inclusion.
- Have another medical condition, acute or chronic, that in the investigator's judgment may increase the risk associated with participation in the study or administration of the investigational product, or that may interfere with the interpretation of the results of the study.
- Have known hypersensitivity to the components of the investigational products.

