7.4.3 Safety variables

- Incidence of unexpected AEs related to the research product. (TE: Visits 1, Final and Safety Call)
- Changes in the MAVC (TE: visits 1 and final).
- Incidence of chemosis (ET: visits 1 and final).

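### Acuity change is evidently to be analysed on the Snellen decimal, which weights equal proportional losses unequally; logMAR from the recorded fraction would weight them equally

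*Combined protocol and SAP*

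**What the plan says.** Section 7.4.4.3 has acuity read on a Snellen chart. The corrected value goes into the clinical record and the electronic case report form (FRCE) as a fraction, and "in addition to the FRCE it will be noted in decimal". The same section gives the conversion (20/20 is 1, 20/40 is 0.5) and the adverse-event rule: "A decrease of more than 2 lines on the Snellen card must be reported and handled as EA".

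The variables table in section 7.4.4 types acuity change as discrete quantitative, gives the normal value as "Fraction 0.6 to 2.0", and assigns "ANOVA for repeated measures" together with one-way ANOVA. Section 7.4.3 lists acuity change at visit 1 and the final visit as a safety variable. Section 3.2 has a secondary objective of non-inferiority in safety "by means of changes in CVAM". Section 5.1.2 sets the lower limit of acuity by excluding patients who "Have a CVAM of 20/200 or worse in one of the eyes".

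Neither logMAR nor any other log transformation of acuity appears in the documents. Section 10.1.2 does not name the scale on which acuity is modelled.

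**The concern.** An ANOVA on change treats a given numerical difference as the same amount of change wherever it occurs. Section 7.4.4.3 defines acuity by the minimum angle of separation, and the decimal is the reciprocal of that angle in relative terms. A fixed proportional loss of resolution is therefore a large decimal change in a good eye and a small one in a poor eye. The adverse-event rule counts chart lines, so the event rule and the mean-change analysis work on different scales.

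At stake is how the mean acuity change behind the section 3.2 safety objective should be read. A group mean in decimal units does not correspond to a fixed proportional loss, or to a fixed number of lines, unless the baseline acuities are known.

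**Working it through.** **Inputs.** From section 7.4.4.3: the fraction-to-decimal conversion; 20/20, 20/40 and 20/200 subtend 5, 10 and 50 minutes of arc; the event rule is more than 2 lines. From section 7.4.4: normal values of 0.6 to 2.0. From section 5.1.2: eyes at 20/200 or worse are excluded. *Assumption:* the documents say only that a Snellen chart is used, so two line layouts are tried below.

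**Formulas.** Decimal = numerator / denominator. Loss = decimal before minus decimal after. logMAR = −log10(decimal).

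**Plan's own figures.** 20/20 = 1.0 and 20/40 = 0.5, as stated. The normal range of 0.6 to 2.0 is labelled a fraction, but the values are decimals: 2.0 is 20/10, and 0.6 is about 20/33.

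**Check that needs no chart layout.** Doubling the angle:
- 20/20 to 20/40 (5 to 10 minutes): 1.0 − 0.5 = 0.50 decimal; log10(2) = 0.30 logMAR.
- 20/100 to 20/200 (25 to 50 minutes): 0.20 − 0.10 = 0.10 decimal; again 0.30 logMAR.

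The same proportional loss counts 0.50 / 0.10 = 5 times as much in the better eye.

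**Layout (a): equal-ratio lines of about 0.1 logMAR (assumed).**

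| One-line loss | Decimal | logMAR | 20/20 step ÷ this step (decimal) |
|---|---|---|---|
| 20/10 to 20/12.5 | 0.400 | 0.097 | 0.5 |
| 20/20 to 20/25 | 0.200 | 0.097 | 1 |
| 20/40 to 20/50 | 0.100 | 0.097 | 2 |
| 20/80 to 20/100 | 0.050 | 0.097 | 4 |
| 20/160 to 20/200 | 0.025 | 0.097 | 8 |

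From 20/10 (the top of the table's range) to 20/160 (the last eligible line on this layout) the ratio is 0.400 / 0.025 = 16. Over all lines of this layout the logMAR step runs only from 0.097 to 0.107, a ratio of 1.1.

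A loss just large enough to be an adverse event is three lines. It equals decimal × (1 − 10^−0.3) = decimal × 0.499. That is 0.50 from a decimal of 1.0 and 0.12 from a decimal of 0.25, and 0.30 logMAR in both.

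**Layout (b): irregular lines 20/10, 15, 20, 25, 30, 40, 50, 70, 100, 200 (assumed).** For eyes at 20/20 or worse, the largest decimal step is 0.200 (20/20 to 20/25) and the smallest is 0.0857 (20/70 to 20/100), a ratio of 2.3. Including 20/10 to 20/15 (0.667) raises it to 0.667 / 0.0857 = 7.8. In logMAR the steps run from 0.079 (20/25 to 20/30) to 0.301 (20/100 to 20/200), a ratio of 3.8. On such a chart logMAR weights equal ratios of acuity equally, but not every printed line.

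**The case against.** The strongest case against has four parts.

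*The plan never says the ANOVA uses the decimal.* This is correct, and the fraction is recorded too. A reader might take the decimal analysis as a stated fact. It is a strong inference: the decimal is the only single-number form the protocol names, and the table's normal range is in decimals. If another scale is meant, the plan still needs to name it.

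*Large individual losses are already caught in lines.* This stands. A loss of more than 2 lines in any eye must be handled as an adverse event. Adverse-event incidence is compared by chi-square or Fisher's test (section 7.4.4) and reported for all randomised patients (section 10.1.2). What is missing is a separate tabulation for acuity: section 7.4.4 lists only ANOVA for it, and Table 3 gives analysis codes without naming a line-loss count.

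*The practical effect may be small.* This also stands. A reader might infer that small shifts in near-normal eyes dominate the mean and hide losses in poorer eyes. The documents give no baseline acuity distribution or standard deviation, so they cannot support that. The population has mild to moderate dry eye, with glaucoma and sight-threatening retinal disease excluded. If most eyes were at 20/40 or better (an assumption), the disparity between one-line steps at 20/20 and at 20/40 would be about 2-fold.

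*LogMAR is not a complete cure.* This stands as well. With irregular chart lines the logMAR steps still differ, and recording by whole lines remains coarse.

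**Conclusion.** The point holds as an inexpensive improvement to a safety analysis. Acuity change is evidently to be analysed on the decimal scale, where equal proportional losses carry unequal weight. The example of 0.20 against 0.05 for the same 0.10 logMAR is exact. It should not be read as a maximum of four: one-line comparisons run from about 2-fold to 16-fold, and the documents fix neither the chart's lines nor the acuity range.

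A reader might go further and conclude that the comparison between arms is biased or invalid. The documents do not support this. The same scale applies to every randomised arm, and nothing shows that a conclusion would change. The effect is on how changes are weighted and interpreted.

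The verdict rests on the inference that the ANOVA uses the decimal. The figures for one-line steps also rest on the assumed chart layouts. The 5-fold result for a doubled angle needs no layout.

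**What to change.** 1. In sections 7.4.4 and 10.1.2, state that acuity is analysed as logMAR, −log10 of the decimal, derived from the recorded Snellen fraction, and that changes and the ANOVA are computed on that scale.
2. Tabulate by arm the number of patients losing more than 2 lines. This reads the result on the same scale as the existing adverse-event rule and covers what logMAR leaves unequal on an irregular chart.
3. State which lines the Snellen chart has, so that a logMAR change can be translated into lines.

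The cost is one derived variable and one table, from data already collected. No new measurement or visit is needed, and the adverse-event rule stays as it is.

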7.4.4.4 TRLNI

For this study, it is required that the TRLNI be taken using the Oculus Keratograph 5M. This topographer has a high-resolution camera that allows the evaluation of the height of the tear meniscus, TRLNI and observation of meibomian glands.

The rings of Placido are reflected on the surface of the cornea, and when a distortion of the reflected sights occurs, it is recorded as a break in the tear film. The software then analyzes this information, and the results are expressed through a color-coded map. The red/orange segments correspond to a shorter rupture time, which will be evidenced in a map showing the total area of the cornea affected by tear film ruptures. The initial breakout time and average time will be displayed in the result presentation.

You will enable the "NIKBUT" button, then select infrared light. The patient will be asked to blink naturally, and when the device is aligned and the message "*Blink twice*" appears, it will prompt them to blink twice. After the second blink, the measurement will automatically start. The patient should keep their eyes open without blinking, as the measurement is automatically interrupted if the patient blinks, moves a lot, or the tear film breaks significantly.

As previously mentioned, a TRLNI of less than 10 sec. Viewpoint

The value of the first break-up time will be recorded in the FRCE under TRLNI. This study may be carried out within a window of 0 to 2 days between the screening visit and the baseline visit, prior to the latter; as well as \pm 2 days with respect to visits 1 and final. It must be carried out at least 2 hours after having applied any stain or drug allowed by this protocol for ophthalmic check-ups.

7.4.4.5 Corneal and conjunctival fluorescein staining

A drop of topical anesthetic will be instilled in the bottom of the conjunctival sac, then a second drop will be applied to the tip of the fluorescein strip, allowing it to sit on the strip for 5 seconds to elute the dye, shaking off the excess at the end. A small contact of the strip is made with the conjunctiva at the fundus of the temporal sac, while the patient looks upwards, without damaging the conjunctiva. It will be graded according to the Oxford scale. [48]

The PI will record in the file and the FRCE the grade granted for fluorescein staining of DO and OS, respectively.

Management as AE: corneal stains that are equal to or greater than grade III will be considered as AEs.

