5.1 Eligibility Criteria

5.1.1 Inclusion criteria

- Can voluntarily give their signed informed consent.
- Be able and willing to comply with scheduled visits, treatment plan, and other study procedures.
- Be of legal age.
- Women of childbearing potential must ensure continued use (initiated \geq 30 days prior to signing the CRF) of hormonal contraceptive method or IUD during the study period.
- Present a diagnosis of mild to moderate dry eye, defined by an OSDI rating \geq 13 and one of the following:
 - o Corneal staining with more than 5 sites.
 - o Conjunctival staining with more than 9 sites.
 - o Tear film breakdown time < 10 seconds.

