7.4.4.6 Conjunctival staining with lysmine green

After the revision with fluorescein, a drop of saline solution will be applied to the tip of the green lysam strip, allowing it to sit on the strip for 5 seconds to elute the dye. A drop of the strip is instilled at the bottom of the temporal sac, while the patient looks upwards, without damaging the conjunctiva. The patient may be asked to blink repeatedly to prevent accumulations in the conjunctival folds. The examination should be done between 1 and 4 minutes after instillation through a neutral density filter or with the red-free filter. It will be graded according to the Oxford scale. [48]

The PI will record in the file and the FRCE the grade granted for fluorescein staining of DO and OS, respectively.

Management as AE: corneal stains that are equal to or greater than grade III will be considered as AEs.

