7.4.4.7 Conjunctival hyperemia

Conjunctival hyperemia is defined as the simplest reaction of the conjunctiva to a stimulus, with a red appearance secondary to vasodilation of the conjunctival vessels of variable intensity. It will be graduated using the Efron scale. [49] See annex 16.3 Efron's scale.

Management as AS: conjunctival hyperemias classified as grade 3 or higher will be considered as AD.

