8.2 Definition of Adverse Event

According to the ICH, an AE is any unfavorable medical appearance in a patient under clinical investigation who is administered a pharmaceutical product, regardless of causal attribution.

Therefore, an EA can be any of the following: any undesirable medical event that is temporally related to the use of a medical product, whether or not it is considered related to such a product; any new illness or exacerbation of an existing disease (worsening of the nature, frequency, or severity of a known condition); relapse of an intermittent medical condition (e.g., headache) not present at baseline; any deterioration in a laboratory value or other clinical test (e.g., electrocardiogram [ECG], x-ray) that is related to symptoms or that results in a change in study treatment or concomitant treatment or discontinuation of study medication.

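### Corneal staining of grade III or more and hyperemia of grade 3 or more count as AEs whatever the baseline grade, so unchanged or improving entry disease can enter AE incidence and blur the between-arm comparison

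*Combined protocol and SAP*

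**What the plan says.** **Absolute rules.** Under fluorescein (7.4.4.5), "corneal stains that are equal to or greater than grade III will be considered as AEs". The lissamine green section (7.4.4.6) carries the same sentence. For hyperemia (7.4.4.7), "conjunctival hyperemias classified as grade 3 or higher will be considered as AD"; AD is read here as AE.

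**Change-based rules beside them.** In 7.4.4.2 the trigger is a rise of at least 40%: an "increase in the baseline OSDI score value should be reported and managed as an AE due to lack of efficacy". In 7.4.4.3, "A decrease of more than 2 lines on the Snellen card must be reported and handled as EA".

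**General definition.** Section 8.2 lists several things that can be an AE. One is "any new illness or exacerbation of an existing disease", glossed as worsening of a known condition.

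**Entry.** In 5.1.1 one of the three alternative qualifying signs is "Corneal staining with more than 5 sites". It is a lower bound only. Nothing in 5.1.1 or 5.1.2 caps the staining or hyperemia grade.

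**Use of the AE data.** Section 3.2 sets a non-inferiority objective on AE incidence. The variable table in 7.4.4 defines incidence as subjects with an AE over subjects exposed, compared by chi-square or Fisher tests. Section 10.1.2 reports AEs in all randomized subjects. Section 7.4.3, however, lists only AEs that are both unexpected and product-related.

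**The concern.** An eye that enters at grade III and stays there has not worsened, and an eye that goes from V to III has improved. As written, both are AEs at each visit where the grade is at or above threshold. The AE count then mixes disease present before the first drop with events arising on treatment.

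Randomization should spread these cases evenly over the arms, but that does not make them harmless. Adding the same background to each arm raises both rates, shrinks the absolute difference and the rate ratio between arms, and for rates below one half increases the variance. At stake are the reported AE incidence of each product and the comparison named in 3.2.

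**Working it through.** The plan gives no figure on this point, so there is nothing to reproduce. The calculation below illustrates size.

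**Inputs from the plan**
- 60 per arm (10.2.1). Section 10.1.4 speaks of 50 evaluable, but AEs are reported for all randomized subjects.
- Alpha 0.05 (10.1.2, sidedness not stated).
- Margin 10%. Section 10.1.2 gives this for the primary efficacy endpoint only; it is borrowed here because no AE margin exists.

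**Assumed inputs**
- Share at or above threshold on entry, b: 0 to 30%.
- True new-AE rates: 20% versus 10%, and separately 10% in both arms.
- Every entry case persists and is counted. This is an upper bound.

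**Formulas**
- Observed rate = b + (1 − b)p, so the difference shrinks by the factor (1 − b).
- SE = √[p₁(1 − p₁)/60 + p₂(1 − p₂)/60], using observed rates.
- Chance of concluding non-inferiority = Φ[(0.10 − d)/SE − 1.645], one-sided 5%, where d is the observed-rate difference.
- Chi-square power: uncorrected Pearson test, two-sided 5%, summed over all binomial outcomes. With 10% versus 20%, expected AE counts are 9 per arm, so 10.1.2 would select chi-square rather than Fisher.

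**Worked case, b = 20%**
- Observed rates: 0.20 + 0.80 × 0.10 = 0.28 and 0.20 + 0.80 × 0.20 = 0.36. The difference is 0.08.
- SE = √(0.28 × 0.72/60 + 0.36 × 0.64/60) = √0.0072 = 0.0849.
- False non-inferiority: Φ(0.02/0.0849 − 1.645) = Φ(−1.41) = 7.9%.
- Equal arms at 10%: both observed rates are 0.28, SE = √(2 × 0.28 × 0.72/60) = 0.0820, and power = Φ(0.10/0.0820 − 1.645) = Φ(−0.43) = 34%.

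**Results**

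| Entry share b | Observed rates (20% vs 10%) | Difference | Chi-square power | False non-inferiority, 10% margin | Power to show non-inferiority, arms equal at 10% |
|---|---|---|---|---|---|
| 0 | 20% vs 10% | 10 points | 33% | 5.0% | 57% |
| 5% | 24% vs 14.5% | 9.5 | 26% | 5.8% | 46% |
| 10% | 28% vs 19% | 9 | 22% | 6.5% | 40% |
| 20% | 36% vs 28% | 8 | 16% | 7.9% | 34% |
| 30% | 44% vs 37% | 7 | 12% | 9.5% | 30% |

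**Direction.** In the planned difference test, the smaller difference and the larger variance both reduce the chance of seeing a true excess. In a margin-based test they work in opposite directions: shrinkage makes a false claim somewhat more likely, while added variance makes a true claim harder to show.

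**The case against.** A reader might infer more than the text supports in five places.

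- **That 8.2 is flatly contradicted.** It is not. Section 8.2 is a list of alternatives, and its first item is any undesirable event temporally related to product use, whether or not causally linked. The absolute rules are in tension with the new-or-worsened item only.
- **That screening findings are themselves AEs.** AEs are evaluated at screening (7.5.1.1), but 7.4.4, 7.4.4.1 and 8.2 tie an AE to a patient who has been given the product. The safer reading is that only grades still at threshold at visit 1 or the final visit count, which is why b + (1 − b)p is an upper bound.
- **That all staining is covered.** Both staining rules say corneal, even in the section headed conjunctival staining.
- **That many patients are affected.** The documents give no share. Patients may qualify on break-up time alone, the diagnosis must be mild to moderate, and 5.1.2 excludes several severe corneal conditions. The share may be small.
- **That the effect always favours a finding of no difference.** This holds for the planned chi-square test, not for a margin-based one.

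Two further objections carry weight. The safety variable in 7.4.3, restricted to unexpected and related AEs, would drop most pre-existing findings; dilution arises under the broader wording of 3.2 and 7.4.4. And the AE comparison is weak anyway, with undiluted power of about one third in this example and no AE margin. Neither removes the misclassification. The investigator's discretion in 7.4.4.1 does not remove it either, since it concerns the general eye examination outside the study variables.

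**Conclusion.** The point holds as a definitional fault. The staining and hyperemia rules ignore baseline, entry grade is uncapped, and nothing in the AE analysis restricts the count to findings that arise or worsen on treatment. Unchanged or improving entry disease can therefore be counted as an AE.

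The numerical effect is uncertain. Under the assumptions shown it runs from modest at an entry share of 5% to more than a halving of chi-square power at 20% or above; the rise in false non-inferiority at a borrowed margin is milder. All of this rests on assumed AE rates and entry shares, on full persistence of entry grades, and on the broad AE definition in 3.2 and 7.4.4 rather than the narrow one in 7.4.3. The correction is worth making because it is cheap and the reported incidence is otherwise hard to interpret.

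**What to change.** 1. Reconcile 7.4.4.5 to 7.4.4.7 with 8.2. For the AE incidence analysis, count a corneal staining or hyperemia finding only when the eye is at the protocol's existing threshold and worse than its own recorded baseline grade, with baseline taken as 7.5.1.1 provides.
2. Tabulate grades already at threshold at baseline separately, by arm, as pre-existing findings.
3. Reconcile the AE incidence of 3.2 and 7.4.4 with the narrower variable in 7.4.3, and state which one the non-inferiority objective uses.
4. Leave safety monitoring and clinical handling of these findings unchanged.

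**Cost.** One sentence in each of three sections, one table, and one clarification. Staining grades are already recorded per eye and both signs are assessed at screening. Section 7.4.4.7 does not say that hyperemia is recorded per eye, so that should be confirmed. The small downside is that persistent high grades leave the AE count; they remain visible in the staining and hyperemia outcomes.
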